5.2.3 Inflammatory bowel disease

6.0 TREATMENT PLAN

6.1 Treatment Overview

6.1.1 Subsection for Radiation Delivery Details

6.1.1.1 Preparation process for radiotherapy

6.1.1.1.1 PET CT and MRI

- The subject will start ADT on the day of or after PSMA-PET/MRI. ADT can be administered at UNC or at Subject's local providers. Prior to radiation planning, the subject will have three MRI-compatible fiducials placed into the prostate by an urologist or radiation oncologist. These will be used for image registration purposes.
- 1-2 weeks after fiducial placement, the subject will undergo PSMA-PET/MRI (pelvis) scan at the BRIC. The subject will be injected with ~0.07 mCi/kg body weight ⁶⁸Ga-PSMA-11. Subject will undergo a PET/MR of the pelvis

CONFIDENTIAL UNIVERSITY OF NORTH CAROLINA July 24, 2024

with simultaneous acquisition of multi-parametric (mp)MR sequences and PET about 60 minutes after radiotracer injection (Siemens Biograph mMR). During the uptake period of 60 minutes, the subject should drink at least 500 mL of fluid (water or fluid of choice). The subject should void immediately prior to PET/MR acquisition. The MR sequences to be acquired are shown in Sequences of the mpMRI protocol). PET/MR acquisition takes A.6 about 30 minutes. Intravenous contrast will be administered for the mpMRI. All PET images will be reconstructed with corrections for attenuation, dead time, random events, and scatter, using iterative ordered-subsets expectation maximization. PET images in PET/MR will be acquired in list mode and reconstructed for several time points after scan start time and durations adjusted for radioisotope decay: e.g. 0-5 min, 5-10 min, 15-21 min and 21-28 min. No Lasix will be used for the PSMA-PET/MRI imaging acquisition. For the first five protocol subjects, if real-time reconstruction does not produce satisfactory images, the option to have the subject void (i.e. urinate) and reimage will be considered.

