6.1.1.1.3 SBRT with CyberKnife

- 1. SBRT with the use of CyberKnife will occur roughly 6 weeks after initiation of EBRT. Standard departmental protocol will be followed for CK-SBRT preparation. Patients with seminal vesicle involvement are eligible and seminal vesicles will be covered with CK-SBRT only as clinical indicated.
- 2. The fusion of the PSMA PET/mpMRI scans with the planning CT will be carried out in the treatment planning software; the fiducials will be used for soft tissue registration. Initially, the T2w MRI sequence will be registered with the planning CT by mutual information registration via fiducials. If necessary, manual adjustments may also be applied during image registration. The PSMA-PET and rest of the MRI and PET-CT scans will share the registration between the T2w MRI scan and planning CT.
- 3. The GTV-MRI will be outlined as a joint effort between a radiologist and the treating radiation oncologist on the basis of the PI-RADs v2 criteria.³⁴⁻³⁵ Additionally, the GTV-PET will be contoured again jointly between the radiologist and radiation oncologist by 30% of the SUVmax value.²⁴ This will be done by taking into account all additional information (including tumor localization in the diagnostic biopsy and physical exam [palpation]). An additional volume (GTV-union) is created from both GTVs.
- 4. The GTVs (i.e. DILs), will be biopsied as a joint effort between the treating radiation oncologist and a urologist. Two cores will be taken per GTV.
- 5. Contouring of the prostate, rectum, and urethral will be performed per UNC standard practice and SBRT with CyberKnife will be performed per UNC standard practice.

- 6. Per UNC standard practice, if the CT or the MRI imaging shows suspicious pelvic nodes, these will be included in the radiation treatment field. If the PSMA imaging alone shows suspicious pelvic nodes, a biopsy of the suspicious node will be offered, and upon confirmation, these may be included in the radiation treatment field.

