6.2 Toxicities and Dosing Delays/Dose Modifications

Any patient who receives treatment on this protocol will be evaluated for toxicity. Each patient will be assessed periodically for the development of any toxicity according to the Time and Events Table (Section 8.1). Patients will be evaluated during their external beam radiation therapy at least once/week while on treatment. Acute toxicity (<3 months) and/or late radiation associated toxicity (>3 months) will be assessed according to the NCI Common Toxicity Criteria for Adverse Events (CTCAE), version 5.0 (if appropriate). Treatment holds and delays and dose adjustments will be made according to the system showing the greatest degree of toxicity per these metrics. Neither dose modifications or treatment delays are anticipated and priority will be given to honoring normal tissue dose constraints (5.1.1.3).

For further information regarding PSMA please refer to the package insert: Galium Ga 68 PSMA-11 Injection

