8.0 EVALUATIONS AND ASSESSMENTS

8.1 Time and Events Table

Study Assessments	Pre- radiation ¹	Radiation Therapy	1, 3, 6, 9, 12 months post- radiation ^{1,3}	2-5 years post- radiation ^{1, 3}
Assessment, consultation	X			
Informed Consent	X			
History and PE ¹	X			X
Performance Status	X			X
Quality of Life ²	X		X	X
Toxicity Evaluations ³	X		X	X ³
PSA Measurements	X		X	X
PSMA-PET/MRI+CT ⁴	X			
CBC, coagulations ⁵ , CMP	X			
Fiducials ⁶		Х		
Radiation planning ⁷		Х		
Androgen deprivation therapy ⁸		Х		
Radiation Therapy ⁹		Х		
Biopsy ¹⁰		Х		

Footnotes to Time and Events Table

- History and physical exam may be performed within 8 weeks prior to day 1 of study treatment. Other evaluations must be performed within 8 weeks priors to Day 1 (D1) of study treatment. Screening labs performed within 8 weeks prior to D1 of study treatment do not need to be repeated on D1. A window of +/- 30 days applies to all study visits unless otherwise specified.
- 2. EPIC-26 (A.4 Quality of Life according to EPIC-26) and PCSI (A.5 The local Quality of Life questionnaire)
- 3. Subject will be regularly followed and seen by the treating physician every 6 months for up to 5 years after treatment. Patients who have an ongoing ≥grade 2 or serious AE (SAE) will continue to be followed until the event is resolved or deemed irreversible by the investigator.
- 4. PSMA-PET/MRI+CT should be no later than the day of starting ADT.
- 5. INR or PT and PTT
- 6. During CK-SBRT, the subject will have MRI-compatible fiducials (e.g. gold) placed into the prostate by the radiation oncologist. These will be used for image guided radiation therapy.
- 7. The irradiation technique will be a combination of EBRT and BT. The highest planning priority will be to satisfy the restrictions of the bowel, rectum and bladder. Refer to Section 6.1.1.3 for additional details including dose on target volumes and planning priorities.
- 8. Androgen deprivation therapy will start no earlier than the same day of the PSMA-PET/CT scan. Duration per standard of care.
- 9. Radiation therapy will consist of:
 - a. 5 weeks of external beam radiation (EBRT). Typically 8 weeks after initiation of ADT.
 - i. Prostate +/- pelvic LNs (determined by radiographic findings): 1.8 Gy/fx x 25fx
 - ii. Regional radiographically pos LNs: 2.25 Gy/fx x 25 fx
 - b. SBRT with CyberKnife
 - i. DIL: 8.0 Gy/fx x 3fx.

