10.0 STATISTICAL CONSIDERATIONS

10.1 Study Design/Study Endpoints

This will be a prospective, single-arm, non-randomized, phase II study to examine the feasibility and acute and late toxicities of standard radiation treatment for unfavorable intermediate and high risk prostate cancer - this involves a combination of external beam radiation therapy and SBRT-CK and androgen deprivation therapy – while using advanced imaging modalities (PSMA/PET-mpMRI) to intelligently adapt the radiation fields. The radiation therapy usually takes 2 months and the follow up is 60 months, while the duration of the evaluation of the final results will be about 12 months after the end of treatment.

There is one primary endpoint:

(1) Late genitourinary toxicity and gastrointestinal toxicity at 12 months (these will be recorded at 1, 3, 6, 9, 12, 24, 36, 48 and 60 months after radiotherapy, according to CTCAE v5).

Table 1 shows an overview of late toxicities in randomized studies of conventionally fractionated schemes in primary prostate carcinoma. On average, the rate of late GI / GU toxicities of grade 2 or higher averaged a rate of approximately 16%.

Study	1 ³⁸	2 ³⁹	3 ⁴⁰	4^{41}	5 ⁴²	6 ⁴³				
Patient #	296	151	101	478	372	1065				
Total dose (Gy)	76	76	75.6	86.4	76	74				
Fractions #	38	38	42	39	38	37				
Dose/fraction (Gy)	2	2	1.8	2	2	2				
Late Reactions – RTOG G2+										
GI (%)	9	22.5	5.1	3.7	8	13.7				
GU (%)	19	13.4	16.5	15.5	24	9.2				

 Table 1 Summary of results from recent clinical trials with external beam radiotherapy.

Table 2 shows an overview of late toxicities in randomized studies of combination external beam radiotherapy and SBRT in primary prostate carcinoma. On average, the rate of late Grade 2 or higher GU toxicities is $\sim 11.4\%$ and for GI toxicities $\sim 6\%$.

Table 2 Summary of results from randomized	clinical	trials	treating	with	combination
external beam radiation therapy and SBRT.					

Study	1 ⁴⁴	2 ⁴⁵	3 ⁴⁶	4 ⁴⁷	5 ⁴⁸	6 ⁴⁹	7 ⁵⁰	8 ⁵¹
Patient #	121	26	76	39	108	48	41	45
EBRT dose (Gy)	45	44	46	45	45-50.4	45	45	45
EBRT Fractions #	25	20	23	25	25-28	25	25	25
CK dose (Gy)	21	18 or 21	18	21	19.5	19 or 21	21	18-21
CK Fractions #	3	3	3	3	3	2	3	3
		Late T	'oxicity –	Grade 2	+			
GI (%)	3.4	4.0	9.3	12.8	5.0	0.0	0.0	13.3
GU (%)	20.6	4.0	1.4	10.3	13.7	27.0	11.0	2.9

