10.2 Sample Size and Accrual

Accrual will take place at UNC. The design as proposed in the above section leads to 80% power at an alpha level of 10%. Taking into account that the dominant intraprostatic lesion (DIL, image-identified tumor in the prostate) can be safely defined in around 75% of the patients, and assuming a 10% patient drop-out (nonevaluable) rate, we will plan to enroll 42 patients in order to achieve the primary objective of this study. Based on a previous study conducted with a similar population, we anticipate averaged accrual of 2 patients per month, corresponding to 21 months to enroll 42 patients out of which we can accrue the 38 evaluable patients for this study.

Sequential boundaries will be used to suspend the trial if excessive grade 4 toxicity of any type, attributed to the treatment under study, is seen. If the study reaches a stopping boundary, it may be terminated by the PI, or submitted to the Data and Safety Monitoring Committee with a description of the failures to date and a rationale for why the study should be continued.

The accrual will be halted if the number of grade 4 toxicities is equal to or exceeds b_n out of n patients with full toxicity follow-up (see table below). This is a Pocock-type stopping boundary that assumes that a grade 4 toxicity rate of 0.05 is acceptable. If the true grade 4 toxicity rate is equal to 0.05, the probability of crossing the boundary is 0.20.

Number of Patients, n 1	2	3	4	5	6	7	8	9	10
Boundary, b _n 1	2	2	2	2	2	2	2	2	2
Number of Patients, n 11	l 12	13	14	15	16	17	18	19	20
Boundary, b _n 3	3	3	3	3	3	3	3	3	3
Number of Patients, n 21	1 22	23	24	25	26	27	28	29	30
Boundary, b _n 3	3	4	4	4	4	4	4	4	4
Number of Patients, n 31	1 32	33	34	35	36	37	38	39	40
Boundary, b _n 4	4	4	4	4	5	5	5		

In addition, grade 3+ toxicity (DLT) will also be monitored. The accrual will be halted if the number of grade 3+ DLTs is equal to or exceeds b_n out of n patients with full toxicity follow-up (see table below). This is a Pocock type stopping boundary that assumes that a DLT rate of 0.30 is acceptable. If the true DLT rate is equal to 0.30, the probability of crossing the boundary is 0.20.

Number of Patients, n 1	2	3	4	5	6	7	8	9	10
Boundary, bn -	-	3	4	4	4	5	5	6	6
Number of Patients, n 11	12	13	14	15	16	17	18	19	20
Boundary, b _n 7	7	7	8	8	9	9	9	10	10
Number of Patients, n 21	22	23	24	25	26	27	28	29	30
Boundary, bn 10	11	11	11	12	12	13	13	13	14
Number of Patients, n 31	32	33	34	35	36	37	38	39	40

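### Both stopping boundaries count only patients with an undefined full toxicity follow-up, so at the planned accrual about 10 to 14 patients (32 on one reading of the grade 4 rule) are enrolled before the first one counts, and the later rows cannot limit enrolment

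*Combined protocol and SAP*

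**What the plan says.** Section 10.2 gives two Pocock-type tables, for n = 1 to 38. One covers grade 4 toxicity of any type attributed to treatment, with 0.05 as the acceptable rate. The other covers grade 3+ DLTs, with 0.30 as the acceptable rate. Each is said to be crossed with probability 0.20 at its acceptable rate. Both take their denominator "out of n patients with full toxicity follow-up". The documents do not define that phrase, do not say how events in patients with incomplete follow-up are treated, and do not cap or pause enrolment while patients are pending.

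The timing inputs are elsewhere:
- Accrual (10.2): "we anticipate averaged accrual of 2 patients per month, corresponding to 21 months to enroll 42 patients".
- Start of ADT (6.1.1.1.1): "The subject will start ADT on the day of or after PSMA-PET/MRI".
- Start of external beam RT (8.1, footnote 9): "Typically 8 weeks after initiation of ADT".
- Length of RT and of follow-up (10.1): "The radiation therapy usually takes 2 months and the follow up is 60 months".
- Acute window (6.2): "Acute toxicity (<3 months) and/or late radiation associated toxicity (>3 months"; the start of that clock is not stated.

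Sections 6.4 and 7.1.4 define a DLT as an acute grade 3+ toxicity attributed to treatment. They also halt accrual when the DLT rate reaches 30%, without any follow-up condition.

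**The concern.** A rule meant to halt accrual for excess toxicity should act when the toxicity is seen. Tied to completed follow-up, it acts only after each patient has passed through the ADT lead-in, RT and the toxicity window. Enrolment continues meanwhile, and accrual is planned to last only 21 months. An event that is already known may therefore not enter the count for months, and part of each table can be read only after all 42 patients are enrolled. Because the key phrase is undefined, the size of the delay depends on who interprets it.

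**Working it through.** **1. The plan's own figures.** I used an exact binomial recursion over the printed boundaries, with a look after every patient from n = 1 to 38 and at most one event per patient. The grade 4 table is crossed with probability 0.195 at rate 0.05, and the DLT table with 0.206 at rate 0.30. Both agree with the stated 0.20. Accrual is 42 / 2 = 21 months, as stated. The thresholds are sound; the question is when they can be read.

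**2. Lag from enrolment to full follow-up.** L = ADT lead-in + RT + toxicity window, in months.
- Acute window from the end of RT: 2 + 2 + 3 = 7. This fits a visit schedule indexed to the end of RT.
- Acute window from RT start: 2 + 3 = 5.
- Grade 4 rule only, follow-up to 12 months after RT: 2 + 2 + 12 = 16.

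As a cross-check on the 7 months, section 6.1.1.1.3 says "SBRT with the use of CyberKnife will occur roughly 6 weeks after initiation of EBRT". Then 8 + 6 + about 1 week (assumed length of SBRT) + 3 months is about 6.5 months, or about 13 patients.

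**3. Enrolment when each row becomes readable.** Enrolled before the first patient counts = 2L. Enrolled when row n is readable = min(42, n + 2L). A row can halt accrual only if n + 2L < 42.

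| Lag (months) | Enrolled before n = 1 counts | Rows that can halt accrual | Rows that cannot |
|---|---|---|---|
| 5 | 10 | 1–31 | 32–38 (7 of 38) |
| 7 | 14 | 1–27 | 28–38 (11 of 38) |
| 16 (grade 4 only) | 32 | 1–9 | 10–38 (29 of 38) |

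**4. Effect on halting, grade 4 table.** The true rate of 15% is my assumption; the documents give none. The probability of crossing by the last usable row comes from the same recursion, without dropout. Mean enrolment counts a trial not halted early as 42.

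| Counting rule | P(halt before 42) | Mean enrolled |
|---|---|---|
| 5-month lag | 79% | 25 |
| 7-month lag | 74% | 28 |
| 16-month lag | 44% | 40 |
| Events counted as they occur | 81% | 24 |

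The last line is a simulation of 40,000 trials, with event times spread evenly from RT start to 3 months after RT (assumed). Its natural comparator is the 7-month line: a gain of 81 − 74 = 7 points, with 28 − 24 = 4 fewer patients enrolled on average.

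**5. DLT table alone.** At an assumed true DLT rate of 45%, the 7-month lag gives 67%, and counting events as they occur gives about 73%. The 16-month lag does not apply, because DLTs are acute by definition. These figures leave out the 30% halt in 6.4 and 7.1.4.

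**The case against.** A reader might infer that at least 14 patients must be enrolled before anything counts. The documents do not support a floor of 14. Section 6.2 does not say when the 3-month clock starts, and counting from RT start gives about 10. Enrolled is also not irradiated: of the 14, about 4 (2 months at 2 per month) are still in the ADT lead-in.

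A reader might infer that the late rows do nothing. On the 7-month reading, 27 of the 38 rows can still halt accrual. Section 10.2 also lets a crossing suspend the trial for excess grade 4 toxicity, with termination or referral to the monitoring committee. When n = 28 is reached at month 21, about 4 patients have not started RT and about 4 more are in treatment, so a late crossing can still matter. What the late rows cannot do is limit enrolment.

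A reader might take the 67% as the protocol's chance of halting for excess DLTs. It is not. The 30% halt in 6.4 and 7.1.4 has no follow-up condition. Even with the 7-month lag imposed on it, that rule would halt before 42 with probability 0.98 to 0.99 at a true rate of 45%, with first looks assumed at n = 1, 5 or 10. It conflicts with a table that treats 0.30 as acceptable, and the passages must be reconciled. It gives no numeric backstop for grade 4.

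There are other safeguards: weekly evaluation during external beam RT (6.2), recording of serious events within 24 hours (9.3.2), and continuous monitoring by the principal investigator with quarterly to annual committee review (9.5). They reduce the risk that an event goes unnoticed, but none carries a numeric trigger for grade 4. The text also does not say outright that pending events are ignored; that is the literal reading of the denominator.

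Finally, Amendment 6 reports early closure for low accrual. At 1 patient per month (assumed) and a 7-month lag, grade 4 halting at a true rate of 15% is 83%, against 85% with no lag. The figures here describe the planned design.

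**Conclusion.** The concern holds in a limited form. The boundaries reproduce their stated error rates, but their denominator is undefined and, read literally, delays a safety halt. The sure part is that under every reading considered at least rows n = 32 to 38 cannot limit enrolment, and at least about 10 patients are enrolled before the first counts. On the reading that best fits the visit schedule, the figures are 14 patients and rows from n = 28.

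The loss for an acute-window reading is modest: about 7 percentage points and 4 patients for grade 4 at an assumed 15%. It is large only if full follow-up is taken to mean 12 months after RT. The grade 4 text leaves that open but does not state it.

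These results assume the planned 2 patients per month, no dropout, and true toxicity rates that the documents do not give.

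**What to change.** In section 10.2, keep the tabulated thresholds and change when they are read. Order patients by start of RT, and trigger a boundary as soon as b_n qualifying events have been recorded among the first n patients, without waiting for those patients to complete follow-up. The count among the first n can only rise, so a boundary is crossed early only if it would have been crossed in the end. With scope unchanged, the crossing probabilities stay at about 0.20.

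State which events qualify for each boundary without narrowing the present scope: acute grade 3+ toxicity attributed to treatment for the DLT table, and grade 4 toxicity of any type attributed to treatment for the other. An acute-only window for the grade 4 rule would drop late events that it now covers, and would change its operating characteristics. State when the acute clock starts. Reconcile the 30% DLT halt in 6.4 and 7.1.4 with the 10.2 table.

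The cost is one or two sentences for the counting rule and prompt event tracking, which 24-hour recording of serious events already largely requires. Sample size and thresholds do not change.

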We denote p the probability that a patient experiences a late grade 2+ GU/GI toxicity. We want p to be small enough to claim the new imaging strategy (PSMA/PET-mpMRI) as feasible with no greater late toxicity. Specifically, the null and alternative hypotheses are:

$H_0: p \ge 0.30 \ vs \ H_1: p \le 0.15$

That is, we accept the claim that the new strategy is safe if the observed toxicity rate is not too high, and hope to reject the claim (H0) with sufficient power when the true toxicity rate is about 20%. With a sample size of 38, we reach 80% power to reject (if we observe ≤ 7 cases with late toxicity) the null hypothesis (H0) at alpha = 0.1. To account for 10% loss follow-up, we will enroll 42 patients to ensure 38 evaluable patients.

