Boundary, b _n 14	14	15	15	15	15	16	17		

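### The DLT stopping entry at n = 36 (15) does not fit the Pocock-type boundary that section 10.2 describes; 16 is the value consistent with the stated crossing probability of 0.20

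*Combined protocol and SAP*

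**What the plan says.** Section 10.2 sets two continuous stopping rules, one for grade 4 toxicity and one for grade 3+ DLTs. The DLT rule, which counts patients whose toxicity follow-up is complete, begins: "The accrual will be halted if the number of grade 3+ DLTs is equal to or exceeds b_n out of n patients with full toxicity". Its basis is described as follows: "This is a Pocock type stopping boundary that assumes that a DLT rate of 0.30 is acceptable". Its operating characteristic is: "If the true DLT rate is equal to 0.30, the probability of crossing the boundary is 0.20".

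The last line of the DLT table covers n = 31 to 38 and reads "Boundary, b _n 14 14 15 15 15 15 16 17". So the boundary is 15 at n = 33, 34, 35 and 36, then 16 at n = 37 and 17 at n = 38. The columns for n = 39 and 40 are blank, and there are none for 41 and 42.

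The grade 4 rule has the same form: "This is a Pocock-type stopping boundary that assumes that a grade 4 toxicity rate of 0.05 is acceptable", and "If the true grade 4 toxicity rate is equal to 0.05, the probability of crossing the boundary is 0.20". Its table also ends at n = 38. On numbers, section 10.1 says "we will enroll 42 patients to ensure 38 evaluable patients".

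Sections 6.4 and 7.1.4 define a DLT as an attributable grade 3 or higher acute toxicity and separately halt accrual once the DLT rate is 30% or more.

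**The concern.** A Pocock-type boundary applies the same tail-probability level at every look, so one constant should generate the whole row. In the DLT row the run of four 15s at n = 33 to 36 stands out, because no other value in the row appears more than three times. If one cell was mistyped, the printed rule is not the rule whose crossing probability is quoted. The table is a decision threshold that the study team and the DSMC would read literally: with exactly 15 DLTs among 36 patients, the printed table halts accrual and the boundary as described does not.

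**Working it through.** **Inputs (all from section 10.2).** Acceptable DLT rate 0.30. Stated crossing probability 0.20. Printed boundaries: none at n = 1 and 2; then for n = 3 to 38: 3, 4, 4, 4, 5, 5, 6, 6, 7, 7, 7, 8, 8, 9, 9, 9, 10, 10, 10, 11, 11, 11, 12, 12, 13, 13, 13, 14, 14, 14, 15, 15, 15, 15, 16, 17. The per-look level is not given, so it is solved for below.

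**Step 1: crossing probability of the printed row.** Let f_n(k) be the probability of k DLTs after n patients without having crossed. Then f_n(k) = 0.70 f_(n-1)(k) + 0.30 f_(n-1)(k-1), and any mass with k ≥ b_n is removed and added to the crossing probability. Run over n = 1 to 38:

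- printed row (b_36 = 15): 0.2058
- same row with b_36 = 16: 0.1999

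The stated 0.20 is therefore reproduced by the row with 16. The printed row rounds to 0.21.

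**Step 2: which constant level generates the table.** For a level a, b_n is the smallest b with P(X ≥ b | n, 0.30) ≤ a. Two cells pin a down:

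- n = 24, printed 11: P(X ≥ 11) = 0.0742, so a must be at least 0.0742. This is the largest tail at any printed boundary other than n = 36.
- n = 16, printed 9: P(X ≥ 8) = 0.0744, so a must be below 0.0744, or the entry would be 8.

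Any a in that narrow band reproduces 37 of the 38 columns, including the absence of a boundary at n = 1 and 2 (tails 0.30 and 0.30² = 0.09).

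**Step 3: the n = 36 cell.**

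- P(X ≥ 15 | 36, 0.30) = 0.0917, above the band
- P(X ≥ 16 | 36, 0.30) = 0.0470, below the band

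So the level gives 16. For 15 to be correct, a would have to be at least 0.0917. The printed boundary minus one would then qualify at n = 4 (tail 0.0837), 11 (0.0782), 16 (0.0744), 19 (0.0839), 22 (0.0916), 27 (0.0798), 30 (0.0845), 33 (0.0884) and 38 (0.0762), and n = 2 would acquire a boundary of 2 (0.09). That would make ten other columns wrong in order to make one right.

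**Step 4: check of the method on the companion table.** The same procedure at a rate of 0.05 with a = 0.0958 reproduces all 38 grade 4 columns. The crossing probability is 0.1946, stated as 0.20.

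**Step 5: effect at higher true rates (printed versus 16 at n = 36).** At 0.35: 0.390 versus 0.378. At 0.40: 0.606 versus 0.591.

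**Step 6: if the tables ran to 42.** Continuing at the same levels, the DLT row would be 17, 17, 18, 18 and the grade 4 row 5 throughout. Over 42 looks the DLT crossing probability is 0.2067 with b_36 = 16 and 0.2111 with b_36 = 15. For grade 4 it is 0.1993.

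**The case against.** The gap is 0.2058 − 0.20 = 0.0058 in a discrete rule quoted to two decimals. The grade 4 table misses its own stated 0.20 by 0.20 − 0.1946 = 0.0054, and nobody would call that wrong. This stands as an argument about size. It does not rescue the cell, because the grade 4 row fits one constant throughout and the DLT row does not.

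The cell would rarely change a decision. Section 10.2 plans 2 patients a month, section 10.1 puts radiation at about 2 months, and section 6.2 takes acute toxicity as under 3 months. If full follow-up means through the acute period, about 2 × (2 + 3) = 10 further patients have been enrolled by the time a patient counts. Then 36 + 10 exceeds 42, so accrual would already be complete when the n = 36 entry is first read. This stands unless accrual is much slower than planned; Amendment 6 records early closure for low accrual. The printed value also stops earlier, not later.

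The per-look level is back-solved, and the table was read from extracted text. Eight values line up with n = 31 to 38, and those at 37 and 38 fit, so a shifted column is unlikely. A single misread digit cannot be excluded from text alone.

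A reader might also infer that the tables are wrong to stop at 38 because 42 patients are treated. The documents do not support that. They say 42 are enrolled to yield 38 evaluable, and both tables count patients with full toxicity follow-up. What remains is a conditional gap: section 8.6 evaluates all irradiated patients for toxicity, so if fewer than four are lost, n can pass 38 with no boundary and no text saying that monitoring has ended. Adding four looks would not be a neutral repair, since 0.2067 is further from 0.20 than the printed row's 0.2058.

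**Conclusion.** The n = 36 entry is inconsistent with the boundary the protocol describes, and 16 is the only value that fits both the constant level of the other 37 columns and the stated 0.20. The size is small: 0.206 against 0.200 at a true rate of 0.30, in the conservative direction, with differences of 0.012 and 0.015 at true rates of 0.35 and 0.40. This assumes that Pocock-type means one binomial tail level at every n, that the rule is checked after each patient from 1 to 38, and that the extracted digit is what the protocol prints.

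It would be too strong to infer that the rule fails its stated operating characteristic in any way that matters. The stated 0.20 is right for the described boundary, and the printed row misses it by about as much as the grade 4 table misses its own. The end of the tables at 38 is a point to clarify, not an arithmetic error.

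The larger inconsistency next to this cell lies in sections 6.4 and 7.1.4. A 30% threshold at n = 36 is met at 11 DLTs (0.30 × 36 = 10.8), whereas the table halts at 15 (15/36 = 42%). These passages contradict each other and have to be reconciled, whichever rule is intended.

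**What to change.** 1. Check the n = 36 DLT entry against the source calculation and reconcile it with the boundary as described. The value consistent with the stated 0.20 is 16. If 15 is intended, keep it, say that it departs from the constant level, and restate the crossing probability as 0.21.
2. Add a sentence stating that monitoring ends at 38 patients with full toxicity follow-up. If the tables are instead extended to the 42 enrolled, restate the crossing probabilities: about 0.207 for DLT (with 16 at n = 36) and 0.199 for grade 4 at the same per-look levels.
3. Reconcile the DLT table with the 30% halting statement in sections 6.4 and 7.1.4, so that the protocol contains one accrual-halting rule for DLTs.

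The cost is one table cell, one sentence on where monitoring ends, and matching wording in two sections. Sample size and the primary analysis are unaffected.
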